### **3.1.2 Dose De-Escalation / Cohort Expansion**

- This trial will begin with a fixed dose of Vicineum 30 mg intravesical (Dose Level 1) administered once weekly for the first 12 weeks. Durvalumab administration will begin after 1 week of Vicineum monotherapy, at 1500mg IV once every 4 weeks.
- In the initial six patients, three subjects at a time will enroll at these doses and schedules (Dose Level 1). Dose-limiting toxicity (DLT) for each subject will be determined during the initial 6-week period that the subject is on treatment (i.e., the DLT period). When all subjects in the initial cohort have been on treatment through the DLT period, all available safety data will be considered in the decision to enroll additional subjects at this dose level, or to de-escalate the doses of the study drugs to Dose Level -1, based on a standard “3 + 3” design (see table below). There will be no dose-escalations in this study.

- After the first six to twelve patients, an additional 18 subjects will be enrolled at the highest dose level at which fewer than 2 of 6 subjects experienced DLT in order to obtain additional safety data and preliminary anti-tumor activity. Treatment at this level will continue as long as the cumulative fraction of patients experiencing DLT is < 1/3.

Dose De-Escalation Schedule	
Dose Level	Dose of IND Agent
Level 1	

• Durvalumab 1500mg IV every 4 weeks

• Vicineum 30 mg intravesically per dose*

Level -1	

• Durvalumab 1500mg IV every 4 weeks

• Vicineum 20 mg intravesically per dose*

\* Vicineum administered weekly during the first 12 weeks of the study, then every 2 weeks thereafter.

Dose de-escalation will follow the rules outlined in the Table below.

If 2 or more DLTs occur at dose level -1, then accrual to the trial will end pending an amendment to consider other dosing options to explore for safety before proceeding to explore efficacy.

Number of Patients with DLT at a Given Dose Level	De-Escalation Decision Rule
0 out of 3	Enter an additional 3 patients at same dose level
1 of 3	

Enter an additional 3 patients at Dose Level 1

• If 0 of these 3 patients experience DLT, enter additional patients at Dose Level 1

• If 1 or more of this group suffer DLT then enter up to 3 patients at the next lowest dose level. Reduce by 1

$\geq 2$	

Enter up to 3 patients at the next lowest dose level.

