## **10.2 SAMPLE SIZE DETERMINATION**

The trial will begin with a 3-patient run-in at the proposed doses of Vicineum and durvalumab (1500mg; 30 mg) and if 0/3 or 1/3 patients have a DLT, then the next 3 patients will also be treated at the full doses of the agents (1500mg durvalumab; 30 mg Vicineum). If 0/6 or 1/6 has a DLT, then the remaining 18 patients will be treated at the full doses if the cumulative fraction of patients experiencing a DLT is <1/3.

If 2 or more patients among 3 to 6 have a DLT at 1500mg durvalumab and 30mg Vicineum, then 3 patients will be enrolled at the lower dose level (1500mg durvalumab and 20mg Vicineum), and if 0/3 or 1/3 patients have a DLT, then the next 3 patients will also be treated at the reduced doses of the agents. If 1/6 has a DLT, then the remaining patients will be treated at the lower dose level of the agents (1500mg durvalumab and 20mg Vicineum) if the cumulative fraction of patients experiencing a DLT is <1/3.

As the secondary endpoint, all the evaluable patients will have determinations of many immune parameters at baseline, 3 months, and 6 months. The changes in the parameters obtained from blood samples will be determined at baseline vs. 3 months, and baseline vs. 6 months. The changes in the parameters obtained from biopsies will be obtained from baseline vs. a single second biopsy at 6 months. A very large number of parameters may be evaluated, and unless more parameters than anticipated are to be evaluated, we will assume that 24 patients will be adequate to evaluate changes in these parameters based on the following. As an illustration, we will assume that a total of 25 paired tests will be considered of equal, primary importance. Paired results from 24 evaluable patients, including those used in the initial run-in portion who are treated at the highest safe dose, will provide 90% power to detect a change from baseline of 1.0 SD of the change (effect size=1.0) using a two-sided 0.002 significance level paired t-test, to allow an overall 0.05 significance level test, applying a very conservative Bonferroni adjustment to the set of approximately 25 paired comparisons. In practice, comparisons of the paired values will likely be performed using a Wilcoxon signed rank test instead of a paired t-test, and a Hochberg adjustment may be used instead of an overly stringent Bonferroni adjustment.

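### The 1-of-3 row of the 3.1.2 decision table names Dose Level 1 (30 mg) where it should say the same dose level, so it misdirects new patients if Level -1 (20 mg) is open

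*Combined protocol and SAP*

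**What the plan says.** The 3.1.2 table takes as its left-hand column "Number of Patients with DLT at a Given Dose Level", so it covers both Level 1 (Vicineum 30 mg) and Level -1 (Vicineum 20 mg). Durvalumab is 1500 mg every 4 weeks at each. The sentence introducing the table says that de-escalation follows it.

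- 0 of 3 with a DLT: "Enter an additional 3 patients at same dose level".
- 1 of 3 with a DLT: "Enter an additional 3 patients at Dose Level 1", and then "If 0 of these 3 patients experience DLT, enter additional patients at Dose Level 1". If one or more of those three has a DLT, the row moves down a level.
- 2 or more with a DLT: move down a level.

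The bullets above the table state "There will be no dose-escalations in this study" and place the expansion at "the highest dose level at which fewer than 2 of 6 subjects experienced DLT". The one Level -1 sentence beside the table deals with 2 or more DLTs there, not with 1 of 3.

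Section 10.2 gives the same design in prose. Level -1 opens "If 2 or more patients among 3 to 6 have a DLT at 1500mg durvalumab and 30mg Vicineum". After 0/3 or 1/3 DLTs at the lower level, "then the next 3 patients will also be treated at the reduced doses of the agents". Sections 10.4.2 and 10.4.4 define the MTD as a level with no more than one DLT among six patients.

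**The concern.** The 0-of-3 row is neutral as to level; the 1-of-3 row is not. At Level 1 this makes no difference, and the table and 10.2 agree. At Level -1 the row sends the next three new patients to 30 mg and, if none of them has a DLT, keeps later patients there. By then 30 mg has already produced 2 or more DLTs among 3 to 6 patients.

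At stake is the dose given to a few new patients, and whether Level -1 can be evaluated at all. With three patients at 20 mg and the next three diverted, Level -1 could not meet the six-patient MTD rule.

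**Working it through.** **Text.** Take one case, 1 of 3 DLTs at 20 mg, and read each rule in turn.

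| Source | Where the next three go |
|---|---|
| 3.1.2 table, 1-of-3 row | 30 mg |
| 3.1.2 bullet barring escalation | not 30 mg |
| 3.1.2 expansion bullet | 30 mg already excluded for expansion (2 or more DLTs) |
| 10.2 | 20 mg |
| 10.4.2 and 10.4.4, MTD rule | six patients are needed at 20 mg |

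The row stands alone against the other four. No footnote limits it to Level 1.

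**How often the row would apply at 20 mg.** The plan states no figure to reproduce and no DLT rate for the combination, so the risks below are assumptions. Let p30 and p20 be the DLT risks at the two levels.

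- A = P(2 or more DLTs among 6 at 30 mg) = 1 - (1-p30)^6 - 6·p30·(1-p30)^5. Two or more among the first three is included, since it already implies 2 or more of 6.
- B = P(exactly 1 of 3 at 20 mg) = 3·p20·(1-p20)^2.
- Row reached at Level -1 = A × B.
- Row's second step (0 of the three at 30 mg, so enrollment continues there) = A × B × (1-p30)^3.

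| p30 / p20 | A | B | Row reached | Second step |
|---|---|---|---|---|
| 5% / 5% | 0.0328 | 0.1354 | 0.0044 | × 0.857 = 0.0038 |
| 10% / 10% | 0.1143 | 0.2430 | 0.0278 | × 0.729 = 0.0202 |
| 20% / 20% | 0.3446 | 0.3840 | 0.1323 | × 0.512 = 0.0678 |
| 20% / 10% | 0.3446 | 0.2430 | 0.0837 | × 0.512 = 0.0429 |
| 30% / 20% | 0.5798 | 0.3840 | 0.2227 | × 0.343 = 0.0764 |

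**Which rows are plausible.** Section 1.2.2.2 reports no DLTs among 64 patients given Vicineum alone at doses up to 30.16 mg, and no rise in treatment-related events with dose. Section 14.2.2.3 gives Vicineum-related Grade 3-4 events in 3%. Section 1.2.1.2 gives durvalumab-related events of Grade 3 or higher in 10.0% of the pooled monotherapy patients, not limited to 6 weeks. None of these is a DLT rate for the combination, and the DLT definition in 3.1.1 is broader than any of them. Still, they favor the first two lines of the table.

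**Effect on the MTD.** Under 10.2, a 1-of-3 result at 20 mg still leads to Level -1 as the MTD if the next three have no DLT, with probability (1-p20)^3. Under the row as written that path is lost. The loss is A × B × (1-p20)^3: 0.0278 × 0.729 = 0.020 at 10%/10%, and 0.0837 × 0.729 = 0.061 at 20%/10%.

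**Whether the row is still live.** The longest run-in under 10.2 is 6 + 6 = 12 patients. The literal faulty path also comes to 6 + 3 + 3 = 12. Sections 2.3.1 and 3 cap the run-in at 12. Section 1.2.3 reports 12-week responses on 12 patients, and the DLT window is 6 weeks.

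**The case against.** The strongest reply is that no careful reader would follow the row at 20 mg. Section 10.2 states the Level -1 rule in full, the same section bars escalation, and the row's last step refers to a lower level that exists only beneath Level 1. On that reading the row is simply the Level 1 rule. This shows that the intended rule can be recovered, and it is why the point is minor. It does not remove the error: the heading covers any dose level, the row above is worded neutrally, 3.1.2 names the table as the rule to follow, and nothing says that 10.2 takes precedence.

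The second reply is that the row is very probably spent, given the 12 patients in 1.2.3. That largely stands. The documents do not say which dose those patients received or whether Level -1 ever opened, and run-in patients who could not be evaluated might have been replaced, so it is not certain.

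The third reply is that the harm is small. If toxicity does not rise between 20 and 30 mg, as the single-agent data suggest, the three diverted patients face no added DLT risk. That also stands. What remains in that case is the breach of the plan's own rules and the unfinished Level -1 cohort.

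**Conclusion.** The point holds as a minor wording error in a dose-assignment table. Applied at Level -1, the 1-of-3 row gives the wrong dose and conflicts with the plan's other rules. At assumed DLT risks of 5% to 10% at both levels it would be reached in about 0.4% to 2.8% of trials, and in 13% at 20%. Larger figures, such as 22% at 30%/20%, need 30 mg to be much more toxic than the documents suggest.

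A reader might infer more than the documents support:

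- That Level -1 lacks a correct rule. Section 10.2 gives one.
- That the whole expansion would run at 30 mg. The row's second step points that way, but the expansion bullet in 3.1.2 excludes a level with 2 or more DLTs among six.
- That treated patients would be moved back up. The row concerns new patients only.
- That the stop for 2 or more DLTs at Level -1 must be rewritten because it states no denominator. Its context points to the run-in, and limiting it would loosen a safety rule. It is no part of this point.

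Level 1 decisions, the sample size, the power and the accrual ceiling of 40 are unaffected.

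**What to change.** In the 1-of-3 row of the 3.1.2 table, replace *Dose Level 1* with *the same dose level* in both places. This matches the 0-of-3 row and adopts the rule already in 10.2.

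The cost is two phrases, which can go into the next amendment with its usual IRB approval. No patients are added and no statistical quantity changes. If the run-in is confirmed as complete, the edit serves only to keep the record consistent and is not urgent.

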### **3.2 DRUG ADMINISTRATION**

In this trial, patients will receive both drugs in certain weeks as specified in the schema. The order of administration will be determined by drug delivery by pharmacy to the day hospital on

the day of administration. Therefore, patients can receive either both drugs concurrently or sequentially without a particular order.

### **3.2.1 Durvalumab**

#### **3.2.1.1 Durvalumab doses and treatment regimens**

The initial dose of durvalumab (Cohort 1) is 1500 mg IV every 4 weeks for up to 52 weeks. Please note, at the end of each maintenance cycle there is a 2 week window in order to allow the patients sufficient time to recover from biopsies prior to continuing treatment. Refer to the schema for a detailed description of Durvalumab administration weeks.

Study treatment should be discontinued prior to 12 months if there is confirmed PD, initiation of alternative cancer therapy, unacceptable toxicity, withdrawal of consent, or if other reasons to discontinue study treatment occur.

Subjects who have a dose interruption due to toxicity at any point in the first 12 months of treatment may resume treatment and complete the 12-month treatment period. For patients without recurrent high grade disease and who are tolerating therapy well, optional maintenance therapy may be continued in the second year. The maintenance dose will be durvalumab 1500 mg administered intravenously once every 3 months to provide an immune boost. During that second year, as per standard of care for high grade disease, cystoscopy and urine cytology will be performed every 3 months. This is depicted graphically in the schema in the optional maintenance section.

No incompatibilities between durvalumab and polyvinylchloride or polyolefin IV bags have been observed. Dose of 1500mg durvalumab (for patients >30 kg in weight) will be administered using an IV bag containing 0.9% (w/v) saline or 5% (w/v) dextrose, with a final durvalumab (MEDI4736) concentration ranging from 1 to 20 mg/mL, and delivered through an IV administration set with a 0.2- or 0.22- $\mu$ m in-line filter.

Add 30.0 mL of durvalumab (MEDI4736) (ie. 1500 mg of durvalumab (MEDI4736)) to the IV bag. The IV bag size should be selected such that the final concentration is within 1 to 20 mg/mL. Mix the bag by gently inverting to ensure homogeneity of the dose in the bag.

For patients who lose weight (<30 kg) during the course of the trial and maintain their enrollment ECOG status, further treatment with durvalumab will be weight based. The dose volume of durvalumab and number of vials needed for the subject to achieve the accurate dose will be calculated according to [Appendix B](#).

Durvalumab will be administered at room temperature (approximately 25°C) by controlled infusion via an infusion pump into a peripheral or central vein. Following preparation of durvalumab, the entire contents of the IV bag should be administered as an IV infusion over approximately 60 minutes ( $\pm$ 5 minutes), using a 0.2, or 0.22- $\mu$ m in-line filter. Less than 55 minutes is considered a deviation.

The IV line will be flushed with a volume of IV solution (0.9% [w/v] saline) equal to the priming volume of the infusion set used after the contents of the IV bag are fully administered, or complete the infusion according to institutional policy to ensure the full dose is administered and document if the line was not flushed.

Standard infusion time is 1 hour. However, if there are interruptions during infusion, the total allowed time should not exceed 4 hours at room temperature. The table below summarizes time allowances and temperatures.

### **Durvalumab hold and infusion times**

Maximum time from needle puncture to start of administration	4 hours at room temperature, 24 hours at 2°C to 8°C
Maximum time for IV bag infusion, including interruptions	8 hours at room temperature

In the event that either preparation time or infusion time exceeds the time limits outlined in the table above, a new dose must be prepared from new vials. Durvalumab does not contain preservatives, and any unused portion must be discarded.

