- 2.1.2.10 The subject has a diagnosis of another malignancy within 2 years before the first dose of study treatment, except for superficial skin cancer, localized prostate cancer on active surveillance, or localized solid tumors deemed cured by surgery and not treated with systemic anticancer therapy and not expected to require anticancer therapy in the next 2 years i.e., while the subject may be taking study treatment.
- 2.1.2.11 Current or prior use of immunosuppressive medication within 28 days before the first dose of durvalumab, with the exceptions of intranasal and inhaled corticosteroids or systemic corticosteroids at physiological doses, which are not to exceed 10 mg/day of prednisone, or an equivalent corticosteroid.
- 2.1.2.12 Active or prior documented autoimmune or inflammatory disorders (including inflammatory bowel disease [e.g. colitis or Crohn's disease], diverticulitis [with the exception of diverticulosis], systemic lupus erythematosus, Sarcoidosis syndrome, or Wegener syndrome [granulomatosis with polyangiitis, Graves' disease, rheumatoid arthritis, hypophysitis, uveitis, etc.]). The following are exceptions to this criterion:

- Subjects with vitiligo or alopecia
- Subjects with hypothyroidism (e.g. following Hashimoto syndrome) stable on hormonal replacement
- Any chronic skin condition that does not require systemic therapy
- Subjects without active disease in the last 5 years may be included but only after consultation with the Principal Investigator
- Subjects with celiac disease controlled by diet alone

2.1.2.13 History of primary immunodeficiency.

2.1.2.14 History of allogeneic organ transplant.

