#### **3.2.1.2 Monitoring of dose administration**

Subjects will be monitored before, during and after the infusion with assessment of vital signs at the times specified in the Schedule of Assessment. Subjects are monitored (pulse rate, blood pressure) every 30 minutes during the infusion period (including times where infusion rate is slowed or temporarily stopped).

In the event of a  $\leq$ Grade 2 infusion-related reaction, the infusion rate of study drug may be decreased by 50% or interrupted until resolution of the event (up to 4 hours) and re-initiated at 50% of the initial rate until completion of the infusion. For subjects with a  $\leq$ Grade 2 infusion-related reaction, subsequent infusions may be administered at 50% of the initial rate. Acetaminophen and/or an antihistamine (e.g., diphenhydramine) or equivalent medications per institutional standard may be administered at the discretion of the investigator. If the infusion-related reaction is Grade 3 or higher in severity, study drug will be discontinued. The standard infusion time is one hour, however if there are interruptions during infusion, the total allowed time from infusion start to completion of infusion should not exceed 4 hours at room temperature, with maximum total time at room temperature not exceeding 4 hours (otherwise requires new infusion preparation).

As with any antibody, allergic reactions to dose administration are possible. Appropriate drugs and medical equipment to treat acute anaphylactic reactions must be immediately available, and study personnel must be trained to recognize and treat anaphylaxis. The study site must have immediate access to emergency resuscitation teams and equipment in addition to the ability to admit subjects to an intensive care unit if necessary.

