### **4.2 EXCLUDED CONCOMITANT MEDICATIONS**

The following medications are considered exclusionary during the study.

1. Any investigational drugs
2. Any concurrent chemotherapy, radiotherapy (except palliative radiotherapy), immunotherapy, biologic or hormonal therapy, including investigational therapy for cancer treatment. Concurrent use of hormones for noncancer-related conditions (e.g., insulin for diabetes and hormone replacement therapy) is acceptable. Subjects who enter the study with low risk prostate cancer and then progress to require androgen-deprivation therapy (ADT) when already enrolled on this trial may continue on trial as per investigator discretion.
3. Immunosuppressive medications including, but not limited to systemic corticosteroids at doses not exceeding 10 mg/day of prednisone or equivalent, methotrexate, azathioprine, and TNF- $\alpha$  blockers. Use of immunosuppressive medications for the management of investigational product-related AEs or in subjects with contrast allergies is acceptable. In addition, use of inhaled and intranasal corticosteroids is permitted.
4. Live attenuated vaccines within 30 days of durvalumab dosing (i.e., 30 days prior to the first dose, during treatment with durvalumab and for 30 days post discontinuation of durvalumab. Inactivated vaccines, such as the injectable influenza vaccine, are permitted.)

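### The durvalumab table allows 8 hours for an interrupted infusion where the text allows 4; the low-dose steroid rule is inverted, and one off-therapy event is worded as off-study

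*Combined protocol and SAP*

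**What the plan says.** **Infusion time.** Section 3.2.1.1 states that, if a durvalumab infusion is interrupted, "the total allowed time should not exceed 4 hours at room temperature". It then presents a table as a summary of the time allowances. In that table the maximum for the bag infusion, interruptions included, is "8 hours at room temperature". Directly below, if the table's limits are exceeded, "a new dose must be prepared from new vials".

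Section 3.2.1.2 repeats 4 hours from start to completion, "with maximum total time at room temperature not exceeding 4 hours", and calls for a new preparation otherwise. The same paragraph says that for a reaction of Grade 2 or lower the infusion may be slowed, or "interrupted until resolution of the event (up to 4 hours) and re-initiated at 50% of the initial rate until completion of the infusion".

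**Steroids.** Section 4.2 item 3 lists among the exclusionary immunosuppressants "systemic corticosteroids at doses not exceeding 10 mg/day of prednisone or equivalent". Its exceptions are inhaled and intranasal use, and this: "Use of immunosuppressive medications for the management of investigational product-related AEs or in subjects with contrast allergies is acceptable". Criterion 2.1.2.11, on use in the 28 days before the first durvalumab dose, makes an exception for "systemic corticosteroids at physiological doses, which are not to exceed 10 mg/day of prednisone" or equivalent. Section 3.6.1 stops investigational product when a patient requires a prohibited medication.

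**Bilirubin DLT.** Section 3.3.2 says that a patient with Grade 2 hyperbilirubinemia in the DLT period stops treatment permanently and leaves the study. Section 3.6.1 lists both a DLT and Grade 2 or greater hyperbilirubinemia as reasons to stop protocol therapy. Section 3.6.2 gives five off-study criteria, which end follow-up; neither event is among them.

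**The concern.** The two infusion limits cannot be read as describing different quantities. Both cover an interrupted infusion at room temperature, and the table is offered as a summary of the text that contradicts it. The replacement rules differ in the same way, one tied to 8 hours and the other to 4. After a mild or moderate infusion reaction with a long pause, pharmacy and nursing staff would have opposite instructions on whether the bag must be replaced.

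The steroid sentence says the reverse of what the eligibility rule implies. It names the low doses as exclusionary and leaves higher doses to the open-ended wording of the list. Read literally together with section 3.6.1, a patient properly enrolled on low-dose prednisone must stop protocol therapy.

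The bilirubin sentence uses the term for ending follow-up where the plan elsewhere only ends treatment. Taken at its word, it would end follow-up for a patient who has just had a DLT.

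**Working it through.** The plan has no calculated figure to reproduce here. The infusion point is elapsed-time arithmetic; the other two are comparisons of text.

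**Inputs for the infusion point**
- Standard infusion time T = 60 minutes, with a tolerance of 5 minutes either way (3.2.1.1).
- Pause p of up to 240 minutes, then restart at half the initial rate (3.2.1.2).
- Limits: 240 minutes (text of 3.2.1.1, and 3.2.1.2) and 480 minutes (table).
- Assumptions: full rate until the reaction at t minutes, one pause, and the remainder at half rate.

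**Total time**

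total = t + p + 2(T − t), which for T = 60 is 120 − t + p minutes.

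With the full pause, p = 240, total = 360 − t:

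| Reaction at | Total | Within 4 h | Within 8 h |
|---|---|---|---|
| t = 0 | 360 min (6.0 h) | no | yes |
| t = 30 | 330 min (5.5 h) | no | yes |
| t = 60 | 300 min (5.0 h) | no | yes |

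Across T = 55 to 65 minutes the range is 4.92 h (T = 55, stopped at the end: 55 + 240 = 295 min) to 6.17 h (T = 65, stopped at the start: 240 + 130 = 370 min). Every case is above 4 hours and below 8.

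**Longest pause that fits each limit, T = 60**
- 4-hour limit: 120 − t + p ≤ 240, so p ≤ 120 + t. That is 2.0 h at t = 0 and 3.0 h at t = 60. Across T = 55 to 65 the range is 1.83 to 3.08 h.
- 8-hour limit: 120 − t + p ≤ 480, so p ≤ 360 + t. That is 6.0 to 7.0 h, so every pause of up to 4 hours fits.

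The two limits therefore give different instructions once the pause passes roughly 2 to 3 hours, which is inside the range that 3.2.1.2 permits.

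**Steroids, side by side**
- Entry (2.1.2.11): up to 10 mg/day prednisone at physiological doses is accepted.
- On study (4.2 item 3): doses not above 10 mg/day are named as exclusionary.
- Exceptions in item 3: product-related adverse events, contrast allergy, inhaled or intranasal use. None covers a patient who entered on a low systemic dose for another reason.
- Consequence (3.6.1): needing a prohibited medication ends protocol therapy.

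Appendix C also treats 10 mg or less as the acceptable level, but it does so for tapering after an immune-mediated event, which item 3 already excepts. The conflict rests on 2.1.2.11.

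**Bilirubin DLT, side by side**
- 3.3.2: off study.
- 3.6.1: off protocol therapy, both as a DLT and as Grade 2 or greater hyperbilirubinemia.
- 3.6.2: not an off-study criterion.
- 3.6 asks for monthly safety visits for 90 days after the last dose before removal from study, and sections 6.1 and 8.2 provide for adverse-event follow-up. The event is already a DLT under 3.1.1. So the term is wrong, but the DLT is counted and safety follow-up is provided for.

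**The case against.** The strongest reply on the infusion is that section 3.2.1.2 already gives the remedy, a new preparation beyond 4 hours, and that staff who follow the shorter limit breach neither rule. Two places say 4 hours against one table cell. Infusion-related reactions are also uncommon: Table 1 in section 14.1.2 gives 49 of 3006 patients (1.6%). If that per-patient rate applied here, the accrual ceiling of 40 would give 40 × 49/3006, about 0.65 patients with any reaction, and fewer with a pause beyond 2 to 3 hours. This is why the point is minor. It does not remove the conflict: the table's own rule requires no new bag until 8 hours, and 3.2.1.2 itself describes restarting and running to completion after a 4-hour pause.

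A further reply is that 4 hours does not settle everything. The table and section 14.1.4 also allow 4 hours at room temperature before the start. If the 4-hour total in 3.2.1.2 includes that hold, a full hold plus a 1-hour infusion is already 5 hours. That is right, and the amendment should say what the total includes.

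On steroids, criterion 2.1.2.11 governs the period before the first durvalumab dose, the separate table of prohibited medications in section 4.2 lists no corticosteroids, and the intent is clear. All true, but the sentence as written still gives the wrong result for an eligible patient.

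On the bilirubin wording, the reply is that nothing follows from it in practice. That largely stands: it is a wrong term only.

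**Conclusion.** The concern holds and is minor. The table's limit is twice the one in the text (8 hours against 4). With a 60-minute infusion, one pause and the remainder at half rate, the longest permitted pause gives 5.0 to 6.0 hours, between the two limits. The documents contain no stability data, so which limit is pharmaceutically correct is unknown and no harm between 4 and 8 hours is claimed.

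The steroid rule is inverted as written and would, read literally, take an eligible patient off therapy. The bilirubin sentence uses the wrong disposition term, with no effect on the DLT count. The documents give no figure for how many patients the last two would affect. None of the three changes the sample size, power or alpha.

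**What to change.** 1. In the section 3.2.1.1 table, change the infusion maximum to 4 hours, matching the text above it and section 3.2.1.2. If the supplier's stability data support 8 hours, use 8 in all three places instead. Beside the sentence on pausing, state that a pause taking the total past the limit needs a new bag, and say whether the total counts the room-temperature hold before the start.
2. In section 4.2 item 3, make the excluded doses those exceeding 10 mg/day of prednisone or equivalent, and keep the listed exceptions.
3. In section 3.3.2, replace removal from the study with removal from protocol therapy, with safety follow-up per section 3.6.

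The cost is three wording corrections in the next amendment and one question to the drug supplier. There is no cost to patients or data.
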